3.8 Justification of choice of study population

We include all patients undergoing video-assisted thoracoscopic procedures, with planned operation time less than 90 minutes e.g. wedge resection, pneumothorax, small nodules in the lung parenchyma, under general anaesthesia, who have an American Society of Anaesthesiologists [ASA] physical status class I to III. Vulnerable patients (children, patients with cognitive impairment and patients with documented dementia) will be excluded from the study. We are interested in the effect of Lidocaine on post-operative pain in thoracic surgery patients because pain could lead to other morbidities.

4. STUDY OBJECTIVES

4.1 Overall Objective

The purpose of this study is to evaluate whether perioperative administration of lidocaine lowers morphine consumption and pain after skin closure until six months post-operative, compared to administration of placebo in participants who have undergone video-assisted thoracoscopic surgery.

4.2 Primary Objective

The primary objective of this study is to determine, whether perioperative administration of lidocaine provides superior analgesia in the early postoperative period (first 24 hours) compared to placebo treatment. This will be measured through total Morphine consumption in mg and pain intensity (VAS) within the first 24 hours, measured at 1 hour, 2 hours, 4 hours, 8 hours, 16 hours and 24 hours after skin closure.

4.3 Secondary Objectives

Secondary Objectives are to determine the effect of Lidocaine on the following, compared to placebo:

- Pain intensity (VAS) and total morphine consumption in mg 1, 2, 4, 8, 16, 24 and 48 hours (\pm 30 minutes) after skin closure
- Length of hospital stay
- Time to first defecation
- Postoperative nausea and vomiting
- 30-day mortality
- Chronic pain

4.4 Safety Objectives

n/a

5. STUDY OUTCOMES

5.1 Primary Outcome

The primary endpoint is a decrease in total morphine consumption (TMC) via PCA of on average 2 mg and a decrease in pain intensity of at least 1.5 units on the VAS, within the first 24 hours measured at 1, 2, 4, 8, 16, and 24 hours after skin closure.

5.2 Secondary Outcomes

- Pain intensity (VAS) and total morphine consumption at 1, 2, 4, 8, 16, 24 and 48 hours after skin closure. Length of hospital stay – Defined as the time (in days) from the date of surgery until the date of discharge.
- Time to first defecation – Defined as the time from skin closure to the time of first defecation.
- Occurrence of nausea and/or vomiting
- Chronic pain – pain intensity (VAS) will be assessed (with and without coughing) 2 weeks (+2 weeks), 3 and 6 months (\pm 7 days) after surgery

5.3 Other Outcomes of Interest

30-day mortality – because pain can lead to serious morbidities and thus mortality, lidocaine may reduce the number of mortalities after surgery.

5.4 Safety Outcomes

n/a

6. STUDY DESIGN

6.1 General study design and justification of design

In this study we will conduct a prospective, randomized, double blind, single centre clinical trial, to evaluate the effect of perioperative lidocaine on postoperative total morphine consumption and postoperative pain in patients undergoing thoracoscopic procedures with operation time inside 90 minutes. Intraoperative analgesia will be given as deemed necessary by the anaesthetist, using fentanyl boli (1-2 µg/kg) as well as continuous infusion of remifentanyl. The following rules need to be applied concerning opioid administration: Before surgical incision administration of at least 4 µg/kg of fentanyl IV, no more than 1 µg/kg of fentanyl per hour IV thereafter; additional analgesia is covered by adjusting remifentanyl infusion; the last dose of fentanyl is administered at least 60 min before the end of the surgical procedure. This should minimize the variability of intraoperative opioid administration during the study. No infiltration of local anesthetics is allowed. At the end of surgery, after haemostasis and if not contraindicated, metamizol 1g will be given IV.

The study addresses the analgesic potential of perioperative lidocaine infusion in addition to the normal analgesia by comparing:

- Lidocaine 2% (LA):
Immediately at anaesthesia induction, bolus injection of lidocaine 1,5 mg/kg approximately 30 minutes before incision, followed by a continuous IV infusion of lidocaine at 3,0 mg/kg/h, until 2 hours after skin closure.
- Placebo (PA) (normal analgesia) :
Same procedure as in the lidocaine arm, but with placebo solution (NaCl 0,9%)

6.2 Methods of minimising bias

6.2.1 Randomisation

Each eligible participant will be allocated to Lidocaine or Placebo treatment using an unstratified block randomisation procedure as implemented in the electronic data capture (EDC) software secuTrial. An allocation ratio of 1:1 and a block size of 8, ensure a balance in sample size across both groups over time.

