6.2.2 Blinding procedures

The treatment assignment is done by the randomization algorithm and recorded in the EDC software secuTrial. The access to secuTrial is password protected and restricted to the trained staff only. The randomizing anaesthesiologist, dedicated study nurse of the department or thoracic surgeon will not be involved in patient care or patient assessment.

The Lidocaine/placebo will be prepared after patient inclusion and randomization in syringes marked with patients study number by the anaesthesiologist or dedicated study nurse of the department that is not participating in surgery (according to the delegation log) just before surgery and storage in a designated cooler until administered. The IMPs data will be recorded in the dispensing log accessible for a potential emergency unblinding.

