7.2 Recruitment and screening

The patients will be recruited by the thoracic surgeons in the Department of Thoracic Surgery, University Hospital Basel. All thoracic surgeons will be informed about the study. Typically, patients are first seen in the ambulatory clinic or in the tumour board. Patients who need to undergo a thoracoscopic procedure will be approached and informed about the study. An informed consent will be obtained and the patients will be screened for eligibility.

The study should take about four years to be completed. Based on our previous experience we expected the presentation of 200 patients per year with the need for elective thoracoscopic procedures. From our experience, we initially expected about 70% of these patients to be eligible and consent to study participation. We therefore calculated a 2 year recruitment period, i. e. a study-duration of one year as additional 6 months for the last follow up. In the meantime we identified an eligibility and consent to study participation of 30 % of our patients. For this reason and due to a not correct monitoring of the storage temperature of the IMP we have to include further patients and extend the recruitment period (study duration) to 3,5 years and additional 6 months for the last follow-up. The deviation from the storage temperature specified in the product information (RT, 15 – 25°C) of IMP (average 26.2°C; 19.2 – 27.9°C) lasted 6 months (20.05.2020 – 09.11.2020). Before May 2020 storage temperature of the IMP was not monitored. We consulted the Manufacturer (Sintetica SA) concerning this issue and got the information that in-house studies (Sintetica SA), which are not available for clients, show, that the IMP will be stable for 6 months at 40°C without influencing IMP quality. Since the initiation of the trial neither events due to safety reasons occurred nor supplementary medical intervention were necessary due to application of IMP stored under elevated temperature. No SAE occurred due to application of IMP. For this reason a threat for study patients can be excluded. Since 13.11.2020 the IMP is stored as in product information described temperature.

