7.3 Assignment to study groups

The assignment of each participant to LA or PA group is done by the anaesthesiologist, dedicated study nurse of the department or thoracic surgeon during the treatment preparation. The randomization procedure is described in section 6.2.1.

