9.3.3 Perioperative (day -1 to day 0)

Randomization by anesthesiologist, delegated study nurse of the department or thoracic surgeon not involved in the patient care or assessment.

Notation of treatment of sequentially numbered patient on drug accountability sheet which is only available for doctor not involved in the care and/or assessment of the patients in the study and on Drug accountability Log for Lidocaine and NaCl

Collection of perioperative data by surgical nurse and study coordinator:

- Surgeon
- Type of surgery
- Date of surgery (day/month/year)
- Duration of Surgery (skin-incision-skin closure) (min)
- Duration of anaesthesia (min)
- Number of trocars
- Intraoperative fentanyl (μg) and Remifentanyl (μg)
- Duration of study medication infusion (min)
- Intraoperative study medication infused (mg) (will be later calculated to avoid unblinding)
- Additional analgesic medication (metamizol,)
- Intraoperative complications

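### A disclosed fixed block size of 8, with no rule keeping those who randomise or can see assignments out of recruitment, leaves allocation concealment unsecured

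*Protocol*

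**What the plan says.** **The sequence.** Section 6.1 describes a "prospective, randomized, double blind, single centre clinical trial". Section 6.2.1 allocates patients "using an unstratified block randomisation procedure as implemented in the electronic data capture (EDC) software secuTrial" and adds: "An allocation ratio of 1:1 and a block size of 8, ensure a balance in sample size across both groups over time". There is thus one running list with one fixed block length. Section 12.5 gives the research team access to the protocol, so the block length is open to recruiters.

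**Who recruits.** Section 7.2: "The patients will be recruited by the thoracic surgeons in the Department of Thoracic Surgery, University Hospital Basel".

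**Who randomises.** Section 7.3 says assignment "is done by the anaesthesiologist, dedicated study nurse of the department or thoracic surgeon during the treatment preparation". Sections 6.2.2 and 9.3.3 name the same three roles.

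**Who prepares the syringes.** Section 6.2.2 gives this to a narrower group: "by the anaesthesiologist or dedicated study nurse of the department that is not participating in surgery". Sections 8.1.3 and 8.8 agree.

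**Who can see earlier assignments.** Section 9.3.3 requires "Notation of treatment of sequentially numbered patient on drug accountability sheet" and limits that sheet to a doctor who takes no part in the care or assessment of the study patients. Section 6.3 lets the anaesthesiologist or thoracic surgeon extract a participant's assignment from the EDC at any time. It lists clinical reasons for doing so and requires a report and documentation.

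**The separation rule.** Section 6.2.2: "The randomizing anaesthesiologist, dedicated study nurse of the department or thoracic surgeon will not be involved in patient care or patient assessment". Recruitment, consent and eligibility screening are not mentioned.

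**The concern.** Blinding and allocation concealment protect different stages. Masked syringes protect care and assessment after allocation. Concealment protects the earlier decision to approach, defer or pass over a candidate. Under permuted blocks of known length, anyone who has seen the earlier allocations in a block has information on the next one, and that information exists before the next patient is approached.

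Here a single profession may hold all three ingredients: the block length, earlier allocations (by randomising or through the EDC) and the choice of whom to approach. The only barrier in the text concerns care and assessment. If enrolment were influenced by a predicted allocation, the arms could differ in patient or procedure type. The two covariates in the primary model (duration of surgery and number of trocars, 11.5.1) would not necessarily remove that difference.

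**Working it through.** The protocol gives no predictability figure, so there is none to reproduce.

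**Inputs**
- Block of 8 at 1:1, so 4 + 4 per block (6.2.1). Write 2m = 8, m = 4. There are C(8,4) = 70 possible blocks.
- Recruitment: 59 patients are needed for 42 evaluable (11.3). The synopsis expands 59 to 113 because only patients treated with correctly stored lidocaine enter the final analysis. Assumption: the other 113 − 59 = 54 are the earlier patients who are not analysed.
- Pace: 200 presenting patients a year, 30 % eligible and consenting (7.2).

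**1. Allocations known with certainty, all earlier ones in the block known**

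An allocation is certain once one arm has used its four places. By position in the block:
- 5th: 2/70 = 0.029
- 6th: 8/56 = 0.143
- 7th: 12/28 = 0.429
- 8th: 1

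The sum is 1.6 of 8, or 20 %. This agrees with 2m/(m+1) = 8/5 and with a listing of all 70 blocks.

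**2. Correct guesses, same knowledge**

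Guessing the under-represented arm (Blackwell–Hodges convergence strategy):

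E(correct) = m + 2^(2m−1)/C(2m,m) − 1/2 = 4 + 128/70 − 0.5 = 5.33 of 8, or 66.6 %, against 50 % under concealment. The listing of all 70 blocks gives the same value.

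**3. Scale in this trial**

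59 × 0.20 = 11.8, so about 12 certain allocations among those recruited for the final analysis. Counting only full blocks from a block start gives 7 × 1.6 = 11.2. For 42 evaluable patients the figure is 42 × 0.20 = 8.4.

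**4. Partial knowledge**

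Simulation of 5,000 trials of 113 patients, block starts known, each past allocation known independently with the stated probability:

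| Share of past allocations known | Correct guesses | Certain allocations in 113 |
|---|---|---|
| All | 66 % | 22.4 |
| Half | 57 % | 1.4 |
| One third | 55 % | 0.3 |
| None | 50 % | 0 |

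Scaled to 59 patients, the half-knowledge case gives 1.4 × 59/113 = 0.7 certain allocations.

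**5. Effect of varying the block size alone**

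In an assumed scheme of concealed, mixed blocks of 4, 6 and 8, a person who sees every past allocation and guesses from the running difference between arms is still right about 68 % of the time. What that person loses is certainty at the end of a block, because block boundaries are no longer known.

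**6. Whether the next slot belongs to the next candidate**

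200 × 0.30 = 60 enrolled a year, or roughly one a week. Screening takes place 1 to 7 days before surgery (9.3.1). If enrolment is evenly spread, few consented patients wait at once, so the next allocation is usually that of the next candidate approached.

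**The case against.** **A known block size predicts nothing by itself.** This is correct. A reader might infer from 6.2.1 that any recruiter who knows the block is 8 can predict allocations. The documents do not support that: the trial is double-blind, allocation comes from password-protected software, and a recruiter who has seen no earlier assignment is right 50 % of the time. Prediction needs someone who has seen earlier allocations, knows where the block starts and recruits the next patient. The protocol permits that combination but does not require it.

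**Surgeons do not draw up the drug.** The wording of 7.3, which places assignment at the time of treatment preparation, might suggest that they do. Sections 6.2.2, 8.1.3 and 8.8 give preparation and labelling only to an anaesthesiologist or study nurse not taking part in the surgery. The surgeon's possible routes to knowledge are randomising and the EDC.

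**Separation already exists.** The accountability sheet is closed to doctors who care for or assess study patients, and this limit reads as trial-wide. Surgeons who recruit usually also do ward rounds and follow-up (9.3.5), so many would be excluded in practice. EDC unblinding must be justified, reported and documented. These safeguards reduce the risk. They do not close it: no sentence names recruitment, consent or screening, and 6.2.2 can be read as applying only to the patient being randomised.

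**Consent precedes randomisation.** True, but the foreknowledge comes from patients already allocated, so it is available before the next consent discussion.

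**Delegation may settle it.** The delegation log may already separate the roles. It is not part of the protocol, and the protocol text leaves the overlap open.

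**Conclusion.** The point stands as a gap in allocation concealment: a disclosed fixed block size combined with role rules that do not keep randomisers, or those who can view assignments, out of recruitment.

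The ceiling is 20 % of allocations certain and 66.6 % of guesses correct, about 12 of the roughly 59 patients recruited for the final analysis. It assumes one person knows every earlier allocation and the start of each block. Because three roles share randomisation, partial knowledge is more plausible; with half known, about 57 % of guesses are correct and fewer than one allocation in 59 is certain.

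Two stronger readings should be avoided. Applying the 20 % to all 113 recruits overstates the exposure of the primary comparison, because patients treated before storage was correctly monitored are not to be analysed. And nothing in the documents shows that selective enrolment occurred or how large a bias in the SIA score would follow. The 30 % in 7.2 combines eligibility and consent and does not measure recruiter discretion.

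**What to change.** 1. **Separate the roles (main measure).** In 6.2.2, 7.3 and 9.3.3, and in the delegation log, state that anyone who randomises, prepares syringes, or has access to the accountability sheet or to EDC assignments does not recruit, consent or screen any trial patient, not only the current one. Have the existing study nurse or a non-recruiting anaesthesiologist randomise. Keep emergency code-break access under 6.3 and log each use.
2. **Conceal and vary the blocks (secondary measure).** For patients not yet randomised, have the CTU use randomly varying block sizes, hold the sizes in a CTU-only document and remove the figure from 6.2.1. This mainly removes end-of-block certainty. It does not replace the first measure, since a person who sees every allocation would still guess well above chance.

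**Cost.** One added rule in three sections, a delegation-log change and a CTU list change. No new staff should be needed, since 7.3 already allows a study nurse or anaesthesiologist to randomise. The downsides are less flexibility in who randomises and a slightly larger possible imbalance between arms. Version 3.2 is dated 14.01.2021 and correct storage began on 13.11.2020, so most patients for the final analysis were probably still to be randomised when this version was written.

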6.2.2 Blinding procedures

The treatment assignment is done by the randomization algorithm and recorded in the EDC software secuTrial. The access to secuTrial is password protected and restricted to the trained staff only. The randomizing anaesthesiologist, dedicated study nurse of the department or thoracic surgeon will not be involved in patient care or patient assessment.

The Lidocaine/placebo will be prepared after patient inclusion and randomization in syringes marked with patients study number by the anaesthesiologist or dedicated study nurse of the department that is not participating in surgery (according to the delegation log) just before surgery and storage in a designated cooler until administered. The IMPs data will be recorded in the dispensing log accessible for a potential emergency unblinding.

6.2.3 Other methods of minimising bias

As both groups are treated exactly the same way we prohibit performance bias. The analgesic potential of Lidocaine is quantified using a VAS (1-10). The post-operative pain will be assessed using the short-form McGill Pain Questionnaire¹⁶ and the quality of recovery questionnaire (QoR-40)¹⁷.

6.3 Unblinding Procedures (Code break)

The anaesthesiologist or thoracic surgeon can unblind each participant at any time by extracting the treatment assignment from the records in the EDC software. The anaesthesiologist or thoracic surgeon will report to the sponsor/principal investigator and document the unblinding process. Unblinding will occur if there are any indications of an allergic reaction, and/or the patients general and/or neurological condition worsens, and/or there are signs of adverse reaction to the medication.

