9.3.4 Data of patient-controlled analgesia (PCA)

- Total morphine consumption (mg)
- Total PCA requests
- Positive PCA requests
- Negative PCA requests
- Pain intensity (VAS Score) – with coughing and when immobile
- Riker sedation agitation scale¹⁸PONV [nausea, present or not; vomiting, number of events]
- Adverse events of lidocaine infusion (light headedness, drowsiness, perioral numbness, visual disturbances, metal taste)
- Additional analgesic medication including dose and time of intake during the hospital stay

9.3.5 Hospital stay and follow up data (postoperative day 1 and 2, follow up 2-4 weeks, 3 and 6 months later)

Daily ward rounds until discharge by the surgeon and his delegates to assess the patient for complications. Follow up is performed by the surgeon and the study coordinator during the visit at our outpatient clinic or per telephone inquiry

- Date of discharge from the hospital (day/month/year)
- Pain intensity [VAS Score] – with coughing and when immobile
- Additional analgesic medication including dose and time/date of intake during the hospital stay

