This is a double-blinded study. In case unblinding is needed in order to determine SUSAR, the treatment allocation should not be disclosed to the investigator, nor to the study staff, in order not to make the subject ineligible.

Assessment of Severity

The SAE terms will be reported according to the Common Terminology Criteria for Adverse Events

(CTCAE, Version 4.0).

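### Section 6.3 makes unblinding mandatory on any sign of an adverse reaction, sets no threshold, does not keep the code-breaker apart from care and assessment, and conflicts with section 10.1.1 for SUSARs

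*Protocol*

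**What the plan says.** Section 6.3 gives three triggers for breaking the code. The first two are in this sentence: "Unblinding will occur if there are any indications of an allergic reaction, and/or the patients general and/or neurological condition worsens". The third follows directly: "and/or there are signs of adverse reaction to the medication". The wording is mandatory. On who acts, the section says: "The anaesthesiologist or thoracic surgeon can unblind each participant at any time by extracting the treatment assignment from the records in the EDC software". That person documents the unblinding and reports to the sponsor or principal investigator.

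Four other places bear on the rule:

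- **Section 6.2.2** says the person who randomises "will not be involved in patient care or patient assessment". It describes the dispensing log as available for a possible emergency code break. Section 8.8 says the same of the accountability sheet, and section 9.3.3 restricts that sheet to a doctor outside care and assessment.
- **Section 9.3.4** lists, among the data recorded with the PCA, "Adverse events of lidocaine infusion (light headedness, drowsiness, perioral numbness, visual disturbances, metal taste".
- **Section 9.3.5** has the surgeon and delegates make daily ward rounds until discharge. On the later visits it says: "Follow up is performed by the surgeon and the study coordinator". Pain is rated at those visits.
- **Section 10.1.1** covers unblinding needed to determine a SUSAR and says that "the treatment allocation should not be disclosed to the investigator, nor to the study staff". The reason given is that the subject would otherwise become ineligible.

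**The concern.** A code-break rule normally ties disclosure to a need: someone has to know the allocation to decide on the patient's care. Section 6.3 ties it to an observation. A sign of adverse reaction is enough, whatever its severity and whether or not knowing the arm would change anything. The protocol itself records five symptoms under the label of adverse events of the study infusion, so a literal reader would break the code for each of them.

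Two things are at stake. First, the allocation could reach people who influence outcomes. Section 9.2.1 allows the PCA setting to be adjusted, the synopsis allows additional metamizol, and surgeons see patients on rounds and at the pain follow-up. If the symptoms are more frequent on lidocaine, code breaks would be related to arm. Second, staff have two instructions for the same serious event. Section 10.1.1 also implies that disclosure may cost a patient's eligibility, and section 6.3 does not say that an unblinded patient stays in the analysis.

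**Working it through.** No figure in the plan depends on this rule, so there is nothing to reproduce. The check compares the sections and then illustrates the size.

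**1. Trigger against stated purpose.** Sections 6.2.2 and 8.8 keep the records available for emergencies. Section 6.3 orders unblinding on any sign of an adverse reaction to the medication. The second set of events is much wider than the first, and nothing in 6.3 narrows it.

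**2. Trigger against recorded symptoms.** Section 9.3.4 attributes its five symptoms to the infusion by its label, so on a literal reading each one meets the third trigger of 6.3. The list is not uniformly trivial: sections 3.2, 8.1.1 and 8.2.1 name somnolence and visual disturbances among signs of central nervous toxicity. Which of them should lead to a code break is a clinical question that this point does not answer.

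**3. Who learns the allocation.** The separation in 6.2.2 applies to the randomising person, and the restriction in 9.3.3 applies to the accountability sheet. Section 6.3 uses the electronic data capture record instead and names two roles without repeating either limit. A surgeon who does rounds or follow-up is therefore permitted, though not required, to be the one who looks.

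**4. When.** The infusion ends 2 hours after skin closure. Of the six primary reading times (1, 2, 4, 8, 16 and 24 hours), four come after that. Discharge and all follow-up pain ratings come later still. A code break during or soon after the infusion would precede most of the outcome data.

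**5. Section 6.3 against section 10.1.1.** By definition a SUSAR is related to the product, so it is also a sign of adverse reaction and triggers 6.3. An anaesthesiologist or thoracic surgeon then learns the allocation. A report goes to the sponsor or principal investigator, and nothing says the allocation is left out of it. Section 10.1.1 withholds the allocation from the investigator and study staff. For a SUSAR both instructions cannot be followed. For symptoms that are not serious and unexpected, 10.1.1 is silent and there is no conflict.

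**6. Illustration of size.** Inputs: 21 evaluable patients per arm (section 11.3) and symptom rates p, which the protocol does not give and which are assumed here. Each patient with a symptom counts as one code break. Expected code breaks = 21 × p. Chance of at least one in an arm = 1 − (1 − p)^21.

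| Assumed rate, lidocaine / placebo | Expected code breaks | Chance of at least one |
|---|---|---|
| 5% / 5% | 1.1 / 1.1 | 0.66 / 0.66 |
| 10% / 5% | 2.1 / 1.1 | 0.89 / 0.66 |
| 20% / 10% | 4.2 / 2.1 | 0.99 / 0.89 |
| 40% / 10% | 8.4 / 2.1 | 1.00 / 0.89 |
| 40% / 20% | 8.4 / 4.2 | 1.00 / 0.99 |

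For example, 21 × 0.10 = 2.1 and 1 − 0.90^21 = 0.89. The first row shows that equal rates give no imbalance.

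**The case against.** The strongest reply is that 6.3 would be read sensibly. It requires a reaction to the medication, which is a judgement, and noting drowsiness on a form does not make that judgement. Drowsiness and light-headedness can also follow anaesthesia and morphine in either arm. This has some force for those two symptoms. It does not rescue the rule, because 9.3.4 itself labels all five as adverse events of the infusion, and staff who do not act on them depart from the text of 6.3.

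A reader might infer more than the documents support:

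- **That lidocaine patients would be unblinded more often.** No rates by arm are given. Section 3.7 says known lidocaine side effects are not expected at this dosage. Its list contains none of the five symptoms in 9.3.4, so it does not settle the matter either way. The imbalance remains an assumption.
- **That treating surgeons would be unblinded.** Section 6.3 permits this but does not say it. The same roles appear in 6.2.2 for a person outside care.
- **That 6.3 and 10.1.1 conflict throughout, so that a metallic taste breaks the blind while a SUSAR does not.** A SUSAR triggers 6.3 as well. The two sections serve different purposes and collide only for SUSARs.
- **That the primary result is directly biased and the trial is no longer double-blind.** The SIA score uses the patient's own pain rating and morphine taken by PCA, with requests recorded by the equipment. Nothing in 6.3 says the patient is told. Staff knowledge would act indirectly.

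**Conclusion.** The point holds as a defect in a stated rule and should be fixed. Section 6.3 is mandatory, has no threshold or need-to-know condition, is wider than the emergency purpose in 6.2.2, and does not separate the code-breaker from care and assessment. For SUSARs it cannot be followed together with 10.1.1. These conclusions rest on the text alone.

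The size is uncertain. At assumed rates of 5% to 40% on lidocaine and 5% to 20% on placebo, a literal reading gives about 1 to 8 code breaks among 21 lidocaine patients and about 1 to 4 among 21 placebo patients. Any relation to arm depends on the rates differing. Any bias would act mainly through PCA adjustment, additional analgesics, time of discharge and follow-up pain ratings.

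**What to change.** Reconcile section 6.3 with sections 6.2.2, 9.3.4 and 10.1.1 so that the code-break trigger agrees with the emergency purpose stated elsewhere, and so that one instruction applies to a SUSAR. Which clinical signs call for a code break is for the investigators to decide. Emergency access for patient care should not be narrowed or delayed.

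Add to section 6.3:

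- The code is retrieved by the already unblinded person outside care and assessment, who exists under 6.2.2 and 9.3.3, and is disclosed only to the physician who needs it.
- The date, time and recipient of each disclosure are recorded.
- A patient whose code has been broken stays in the ITT primary analysis of section 11.5.1. The remark on ineligibility in 10.1.1 is brought into line with this.

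The cost is a wording amendment and a short record for each code break. No new role, visit or assessment is needed, and the sample size is unaffected.
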